7.4.3. Laboratory Measurements

Laboratory data will be summarized for each laboratory test listed in [Attachment 9.4.1](#).

7.4.3.1. Treatment Period

Descriptive statistics (N, mean, standard deviation, median, and range) will be reported for each continuous laboratory analyte at DB baseline, OL baseline, each post-OL baseline time point, and endpoint for observed actual value as well as change from DB baseline and OL baseline, respectively. Categorical results (eg, urinalysis tests) will be summarized at DB baseline, OL baseline, each post-OL baseline visit, and endpoint by analysis group using frequency and percentage. All lab values will be presented in the data listings.

Results for glucose and lipid tests (HDL cholesterol, LDL cholesterol, total cholesterol, and triglycerides) will be presented separately by fasting status, which includes fasting only and overall (fasting, non-fasting, or unknown).

The normal reference ranges for laboratory tests will be used to determine whether the laboratory test value is below, within, or above the normal range. Shifts from DB baseline and shift from

322

OL baseline over time will be produced by analysis group to show the percentage of subjects with laboratory test values below, within, and above the normal range. Criteria for Markedly Abnormal Laboratory Values (MALV) per International System of Units (SI) unit of selected laboratory parameters can be found in [Table 6](#). Equivalent MALV criteria for conventional unit are provided in [Attachment 9.4.2](#). The criterion of MALV is satisfied if a value falls into the markedly abnormal range at an assessed visit or if subjects have experienced at least once MALV in the open-label treatment period. The number and percentage of subjects with a particular MALV at each OL visit, endpoint, and during the open-label treatment period (treatment emergent, up to and including endpoint), will be presented by analysis group.

Table 6: – Criteria for Markedly Abnormal Laboratory Values (MALV) (SI Unit)

Laboratory Test	Criteria for Markedly Abnormal Status	
	Low	High
Hematology		
Hematocrit	Male: ≤ 0.37 Female: ≤ 0.32	Male: ≥ 0.60 Female: ≥ 0.54
Hemoglobin	Male: ≤ 115 g/L Female: ≤ 95 g/L	Male: ≥ 190 g/L Female: ≥ 175 g/L
RBC	$\leq 3.5 \times 10^{12}$ /L	$\geq 6.4 \times 10^{12}$ /L
Total WBC Count	$\leq 2.8 \times 10^9$ /L	$\geq 16 \times 10^9$ /L
Basophils	N/A	$\geq 10\%$ $\geq 1.6 \times 10^9$ /L
Eosinophils	N/A	$\geq 10\%$ $\geq 1.6 \times 10^9$ /L
Lymphocytes	N/A	$\geq 75\%$ $\geq 12.0 \times 10^9$ /L
Monocytes	N/A	$\geq 15\%$ $\geq 2.4 \times 10^9$ /L
Neutrophils	$\leq 15\%$ $\leq 0.42 \times 10^9$ /L	$\geq 85\%$ $\geq 13.6 \times 10^9$ /L
Platelet Count	$\leq 75 \times 10^9$ /L	$\geq 700 \times 10^9$ /L
Chemistry		
Albumin	≤ 25 g/L	N/A
ALP	N/A	$\geq 3 \times$ ULN
AST	N/A	$\geq 3 \times$ ULN
ALT	N/A	$\geq 3 \times$ ULN
Bicarbonate	≤ 16 mmol/L	≥ 35 mmol/L
Calcium	≤ 2.05 mmol/L	≥ 2.99 mmol/L
Chloride	≤ 90 mmol/L	≥ 118 mmol/L
Creatinine	N/A	≥ 176.8 μ mol/L
Glucose (fasting)	≤ 2.22 mmol/L	≥ 9.71 mmol/L
Inorganic Phosphorus	≤ 0.5 mmol/L	≥ 1.7 mmol/L
Magnesium	≤ 0.6 mmol/L	≥ 1.15 mmol/L
Potassium	≤ 3 mmol/L	≥ 6 mmol/L

322

Laboratory Test	Criteria for Markedly Abnormal Status	
	Low	High
Sodium	≤ 126 mmol/L	≥ 156 mmol/L
Total Bilirubin	N/A	≥ 34.2 μmol/L
Total Protein	≤ 45 g/L	≥ 100 g/L
Uric Acid	Male: N/A Female: N/A	Male: ≥ 625 μmol/L Female: ≥ 506 μmol/L
Urea (BUN)	N/A	≥ 11 mmol/L
Lipids panel		
Total Cholesterol (fasting)	N/A	≥ 7.77 mmol/L
LDL Cholesterol (fasting)	N/A	≥ 5.18 mmol/L
HDL (fasting)	≤ 1.036 mmol/L	N/A
Triglycerides (fasting)	N/A	≥ 3.39 mmol/L
HbA1c	N/A	≥ 7.5%
Urinalysis		
Urine Blood	N/A	≥ 1+
Urine Glucose	N/A	≥ 3+
Urine Ketones	N/A	≥ 2+
Urine Protein	N/A	≥ 2+

Note: ULN = Upper Limit of Normal; N/A = Not Applicable

A listing of subject data for those who have experienced at least once MALV during the open-label treatment period will be generated. Urine drug screen results will be presented for each parameter by DB baseline, OL baseline, post-OL baseline visit, and endpoint. Number and percentage of positive and negative results will be displayed. Summary statistics of laboratory outputs will be generated per conventional unit and SI unit, separately.

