4. INTRODUCTION

4.1. Background

Binge eating disorder (BED) is a neuropsychiatric disorder characterized by recurrent episodes (on average at least once per week for 3 months) of excess food consumption during a limited time period, accompanied by feelings of loss of control and distress in the absence of regular compensatory behaviors characteristic of bulimia nervosa (BN) (Diagnostic and Statistical Manual of Mental Disorders, 5th Edition [DSM-5]). BED is the most common eating disorder in the United States and Western Europe, with an estimated lifetime prevalence of 2.5% in adults (~3.5% in adult women, 2.0% in adult men, and 1.6% in adolescents) and a mean age of onset of 25.4 \pm 1.2 years (McElroy-2012, Kessler-2013, Hudson-2007). Binge eating disorder is defined in DSM-5 as:

- Recurrent episodes of binge eating characterized by both:
 - Eating an amount of food larger than what most people would eat, in a discrete period of time (eg, 2 hours)
 - Sense of lack of control over eating episode
- Binge-eating episode associated with ≥ 3 :
 - Eating much more rapidly than normal
 - Eating until uncomfortably full
 - Eating large amounts when not feeling hungry
 - Eating alone because of embarrassment
 - Feeling disgusted with oneself, guilty afterward
- Marked distress regarding binge eating is present
- Binge eating occurs, on average, at least once a week for 3 months
- Not associated with recurrent use of compensatory behavior (eg, bulimia nervosa).

Patients with BED show significantly higher prevalence or risk for a range of comorbid psychiatric and medical disorders when compared to healthy individuals. The majority of patients fulfill Diagnostic and Statistical Manual of Mental Disorders, 4th Edition (DSM-IV) criteria for one or more psychiatric disorders, including depression, anxiety, and phobias. BED patients also have a 2-3 fold greater risk for physical ailments, including obesity, hypertension, diabetes mellitus, and chronic pain. Taken together, these findings signify that BED presents a major public health problem with significant social and economic consequences (Kessler-2013). Considering the severity of clinical symptomology, the negative impact on quality of life and physical measures of health, there is a significant need for safe and efficacious treatments for adults with BED.

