6.1.5. Aggregated Analysis Timepoint

An aggregated analysis timepoint named as ‘any OL treatment period (treatment emergent)’ will be derived for selected safety assessments (eg, the worst case analysis) as below.

- Any OL treatment period (treatment emergent): defined as any assessment collected in open-label treatment period (see [Section 6.1.1.1](#)).

Specifically, the aggregated analysis timepoint of any OL treatment period (treatment emergent) will be applied on the following worst-case analysis:

- Markedly Abnormal Laboratory Values (MALV) ([Section 7.4.3.1](#), [Table 6](#))
- Markedly Abnormal Vital Signs (MAVS) ([Section 7.4.5.1](#), [Table 9.1](#))
- QTc prolongation ([Section 7.4.4.1](#), [Table 7](#))
- ECG abnormality ([Section 7.4.4.1](#), [Table 8](#)).
- C-SSRS ([Section 7.4.7](#))

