7.4.4.1. Treatment Period

Descriptive statistics (eg, mean, SD, median, range, 95% CI) for observed actual value at the DB baseline, OL baseline, each post-OL baseline visit, and endpoint and changes from DB baseline and OL baseline, respectively will be displayed for continuous variables (ie, HR, QRS, QTcF, etc) by analysis group.

The overall ECG assessment is conducted by central reading and a determination is made whether the reading is normal (or absent if applicable) or abnormal). Shifts from OL baseline and Shifts from DB baseline over time will be produced by analysis group.

Bazett and Fridericia corrected QT_c values will be classified as having QT_c prolongation according to [Table 7](#).

Table 7: – QTc Prolongation

QTc Prolongation
> 450 msec for males
> 470 msec for females
> 480 msec
> 500 msec
Increase from OL baseline QTc ≥ 30 msec
Increase from DB baseline QTc ≥ 30 msec
Increase from OL baseline QTc ≥ 60 msec
Increase from DB baseline QTc ≥ 60 msec

The number and percentage of subjects having a QT_c prolongation using Fridericia correction method for DB baseline, OL baseline, post-OL baseline visit, endpoint, and any open-label treatment period (treatment emergent, the worst case), will be summarized by analysis group. A listing of ECG data for subjects with at least one prolonged QT_c will also be produced.

For other ECG parameters, subjects are classified as normal or abnormal using the limits specified in [Table 8](#). For abnormal ECG parameter reporting, counts and percentages of subjects will be presented for DB baseline, OL baseline, each post-OL baseline visit, endpoint, and any open-label treatment period (treatment emergent) by analysis group.

Table 8: – Definition of Abnormal ECG Values by Parameter

ECG parameter (unit)	Abnormally Low	Abnormally High
HR (bpm)	≤50	≥100
PR interval (msec)	N/A	≥210
QRS interval (msec)	N/A	≥120
QT interval (msec)	N/A	> 500

Note: N/A = Not Applicable

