Emergence of Serious Suicidal Ideation		No suicidal ideation at DB Baseline, and any serious suicidal ideation [ideation score of 4 or 5] in ‘any extension visit (treatment emergent)’
Emergence of Suicidal Behavior		No suicidal behavior at DB Baseline, and any type of suicidal behavior in ‘any extension visit (treatment emergent)’
Emergence of Suicidality		No suicidality at DB Baseline, and any suicidality in ‘any extension visit (treatment emergent)’
Worsening of Suicidal Ideation		Most severe suicidal ideation in ‘any extension visit (treatment emergent)’ is more severe than the most severe value at DB Baseline
^(a) : Definition of DB Baseline: see Table 12 in SEP360-221 SAP and Table 12 in SEP360-321 SAP; ^(b) : see Table 10 .		

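### For criteria with absolute limits only, the SAP's 'treatment emergent' counts of marked laboratory, ECG and vital-sign values include abnormalities already present before dasotraline.

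*SAP*

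**What the plan says.** SAP 6.1.5 sets up one aggregated timepoint for the worst-case safety analyses: "Any OL treatment period (treatment emergent): defined as any assessment collected in open-label treatment period". It applies this to markedly abnormal laboratory values (MALV), markedly abnormal vital signs (MAVS), QTc prolongation, ECG abnormality and the C-SSRS.

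- **Laboratory (7.4.3.1, Table 6).** The rule is "The criterion of MALV is satisfied if a value falls into the markedly abnormal range at an assessed visit", or at least once in the period. Counts are planned at each open-label visit, at endpoint and "during the open-label treatment period (treatment emergent, up to and including endpoint), will be presented by analysis group". Baseline is not among the timepoints. Shifts from DB and OL Baseline are planned "to show the percentage of subjects with laboratory test values below, within, and above the normal range".
- **ECG (7.4.4.1, Tables 7 and 8).** Some QTc rows are absolute. Others require a rise, for example "Increase from OL baseline QTc ≥ 30 msec". Table 8 is absolute throughout. Its counts are shown at DB baseline, OL baseline, each later visit, "endpoint, and any open-label treatment period (treatment emergent) by analysis group".
- **Vital signs (7.4.5.1, Table 9.1).** Absolute rows sit beside rows that require a change from baseline. Counts are shown at both baselines and on treatment.
- **C-SSRS (7.4.7, Table 11).** Emergence has its own rule, for example "No suicidal behavior at DB Baseline, and any type of suicidal behavior in" the extension visits.

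**The concern.** The label treatment emergent normally tells a reader that something was absent before treatment and appeared on it. As defined here it says only that the value was collected in the open-label period. A subject with fasting HDL of 1.0 mmol/L at DB Baseline, OL Baseline and every later visit meets the Table 6 limit (1.036 mmol/L or below) and is counted as treatment emergent, although nothing changed.

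Changes in laboratory results, ECGs and vital signs are part of the primary safety objective, and the study has no control arm from which to read off background abnormality. The Protocol's own background section says "BED patients also have a 2-3 fold greater risk for physical ailments, including obesity, hypertension, diabetes mellitus, and chronic pain", so some subjects may well bring persistent abnormal values into the study. If new and old cases share one count, background disease can be read as a drug effect, and a real new signal cannot be told apart from it.

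**Working it through.** **Step 1. Which criteria carry a baseline condition?** 'Absolute' here means that the criterion makes no reference to the subject's own earlier value. Multiples of the upper limit of normal and the orthostatic rows are therefore included.

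| SAP table | Rows or analytes | No baseline condition | Change from baseline required |
|---|---|---|---|
| 6, laboratory | 36 | 36 | 0 |
| 7, QTc | 8 | 4 (>450 male, >470 female, >480, >500 msec) | 4 (rise of at least 30 or 60 msec from OL or DB baseline) |
| 8, other ECG | 4 | 4 (HR, PR, QRS, QT) | 0 |
| 9.1, vital signs and weight | 11 | 6 (SBP, DBP, pulse; three orthostatic) | 5 (SBP, DBP, pulse, weight, temperature) |

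The problem is confined to the third column.

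**Step 2. Can other planned tables separate new from old?**

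- *Laboratory.* No MALV count is planned at either baseline. The shift tables use below, within and above normal. Where the marked limit lies beyond the normal limit, a subject who moves from mildly to markedly high and one who is markedly high throughout both appear as high to high. Urinalysis results are tabulated at both baselines, but only as group frequencies. Listings hold the raw values, but a reader would have to rebuild each subject's history by hand.
- *ECG and vital signs.* Baseline counts are shown, so the background is visible for the group. The subject-level split is not: equal counts before and during treatment could be the same people or different ones.

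**Step 3. Which baseline is before dasotraline?** For Pbo-Das subjects, both DB and OL Baseline precede the drug. For Das-Das subjects, OL Baseline is the Week 12 visit of the core study, after randomisation to dasotraline and with no break in treatment (Protocol Table 2, footnote c), so only DB Baseline precedes the drug. In addition, SAP 6.1.1.1 starts their open-label period on the OL Baseline visit date, so that visit's own value can enter the treatment-emergent count.

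**Step 4. How large could it be?** The documents give no figure to reproduce, so this is an illustration on assumed inputs. Let p be the share meeting a criterion before dasotraline, s the share of those who meet it again on treatment, and q the new incidence among the rest.

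Reported rate = s·p + q·(1 − p). Rate among subjects at risk = q.

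With s = 0.80 and q = 0.03:

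| p | Calculation | Reported | Ratio to 3% | Pre-existing share of reported cases |
|---|---|---|---|---|
| 0.5% | 0.0040 + 0.0299 | 3.4% | 1.13 | 12% |
| 1% | 0.0080 + 0.0297 | 3.8% | 1.26 | 21% |
| 10% | 0.0800 + 0.0270 | 10.7% | 3.6 | 75% |
| 20% | 0.1600 + 0.0240 | 18.4% | 6.1 | 87% |
| 30% | 0.2400 + 0.0210 | 26.1% | 8.7 | 92% |

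A second set of assumptions (q = 2%, s from 50% to 90%, p from 1% to 20%) gives reported rates from 2.5% to 19.6% against 2.0%. In both sets the distortion is small for criteria rare at baseline and dominant for common ones.

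**The case against.** The strongest reply has four parts.

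1. *The label is openly defined as a period.* SAP 6.1.5 says what it means, and the C-SSRS uses the same timepoint without a baseline condition. The emergence endpoints in Table 11 are an addition to it. The adverse-event rule is not purely onset or worsening either: SAP 7.4.2 also admits earlier events on attribution to study medication. This is correct, so the SAP is not breaking its own rule. What stands is that the C-SSRS received that extra step and the absolute laboratory, ECG and vital-sign criteria did not.
2. *The Protocol promises no more.* Its section 15.3.3.3 asks only for the number and percentage of subjects with markedly abnormal values, and the changes named in the primary objective are covered by the change and shift tables. This is also correct. It defends the count, but not the name given to it.
3. *Much is already protected or visible.* Half the QTc rows and 5 of the 11 rows in Table 9.1 require a change from baseline, the ECG and vital-sign tables show baseline counts, and urinalysis has baseline frequencies. A reader might infer that every marked laboratory, ECG and vital-sign row is affected. The tables do not support that.
4. *Baseline prevalence may be low.* Protocol 8.2 (exclusion 4) and 12.2 can bar subjects with clinically significant abnormalities at OL Baseline, and 10.3.1 prohibits insulin and liraglutide. High prevalence is doubtful for limits such as ALT of at least 3 times ULN or potassium of at least 6 mmol/L. These entry rules depend on investigator judgement and may well not remove low HDL, but they do rule out treating a high prevalence as given.

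**Conclusion.** The point holds for criteria with absolute limits only, and most clearly for laboratory values. Followed as written, the SAP reports persisting pre-dasotraline abnormalities as treatment emergent. For laboratory tests no planned summary table separates them from new ones, and urinalysis offers only group frequencies at baseline.

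The size is unknown. On an assumed 3% new incidence and 80% persistence, the reported rate is about 3.8% at 1% baseline prevalence and 10.7% at 10%. A reader might go further and infer a fixed multiple, or that pre-existing disease will make up most of these rows. The documents support neither: they give no baseline prevalence for any criterion, and the Protocol's statement about comorbidity is a relative risk of diagnoses, not the frequency of values beyond the marked limits.

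The study is descriptive, so no test or sample size is affected. What is affected is how the primary safety output of an uncontrolled study will be read. That makes this a change worth making before database lock.

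**What to change.** In SAP 6.1.5, 7.4.3.1, 7.4.4.1 and 7.4.5.1:

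1. Rename the present worst-case count 'any occurrence in the OL period' and keep it.
2. Add DB Baseline and OL Baseline rows to the MALV table, as the ECG and vital-sign tables already have.
3. For the absolute criteria, add a treatment-emergent count: subjects who meet the criterion at an on-treatment assessment after OL Baseline and did not meet it at the pre-dasotraline baseline. The denominator is subjects who did not meet it at that baseline and have a post-baseline value.
4. Use DB Baseline as that reference for Das-Das, with OL Baseline as a secondary reference. Use OL Baseline for Pbo-Das, with DB Baseline also shown. Using OL Baseline alone for everyone would hide abnormalities in Das-Das subjects that arose on drug in the core study and persisted.
5. State which baseline Table 9.1 means.

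The cost is SAP wording and some programming on data already collected. Denominators shrink for criteria that are common at baseline: with the planned 500 subjects, to 495 at 1% prevalence and 450 at 10%, before any loss for missing post-baseline values.

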7.4.3.2. Withdrawal Period

Laboratory data will be summarized by presenting descriptive statistics of actual values, change from DB baseline and OL baseline, and changes from withdrawal baseline by visit and analysis group.

7.4.4. ECG Evaluations

As a part of each ECG, heart rate (HR), axis, and the following intervals will be measured: RR, PR, QRS, and QT. Corrected QT intervals (QT_{cB} and QT_{cF}) values are based on the following formula:

- Bazett: $QT_{cB} \text{ (msec)} = QT \text{ (msec)} / (RR/1000)^{1/2}$
- Fridericia: $QT_{cF} \text{ (msec)} = QT \text{ (msec)} / (RR/1000)^{1/3}$

where RR will be reported in milliseconds (msec).

7.4.4.1. Treatment Period

Descriptive statistics (eg, mean, SD, median, range, 95% CI) for observed actual value at the DB baseline, OL baseline, each post-OL baseline visit, and endpoint and changes from DB baseline and OL baseline, respectively will be displayed for continuous variables (ie, HR, QRS, QTcF, etc) by analysis group.

The overall ECG assessment is conducted by central reading and a determination is made whether the reading is normal (or absent if applicable) or abnormal). Shifts from OL baseline and Shifts from DB baseline over time will be produced by analysis group.

Bazett and Fridericia corrected QT_c values will be classified as having QT_c prolongation according to [Table 7](#).

Table 7: – QTc Prolongation

QTc Prolongation
> 450 msec for males
> 470 msec for females
> 480 msec
> 500 msec
Increase from OL baseline QTc ≥ 30 msec
Increase from DB baseline QTc ≥ 30 msec
Increase from OL baseline QTc ≥ 60 msec
Increase from DB baseline QTc ≥ 60 msec

The number and percentage of subjects having a QT_c prolongation using Fridericia correction method for DB baseline, OL baseline, post-OL baseline visit, endpoint, and any open-label treatment period (treatment emergent, the worst case), will be summarized by analysis group. A listing of ECG data for subjects with at least one prolonged QT_c will also be produced.

For other ECG parameters, subjects are classified as normal or abnormal using the limits specified in [Table 8](#). For abnormal ECG parameter reporting, counts and percentages of subjects will be presented for DB baseline, OL baseline, each post-OL baseline visit, endpoint, and any open-label treatment period (treatment emergent) by analysis group.

Table 8: – Definition of Abnormal ECG Values by Parameter

ECG parameter (unit)	Abnormally Low	Abnormally High
HR (bpm)	≤50	≥100
PR interval (msec)	N/A	≥210
QRS interval (msec)	N/A	≥120
QT interval (msec)	N/A	> 500

Note: N/A = Not Applicable

7.4.4.2. Withdrawal Period

ECG data will be summarized by presenting descriptive statistics of observed values, change from DB baseline and OL baseline, and changes from withdrawal baseline by visit and analysis group.

7.4.5. Vital Signs, Weight, and BMI

7.4.5.1. Treatment Period

Descriptive statistics (mean, SD etc.) will be provided for observed at the DB baseline, OL baseline, post-OL baseline visit, and endpoint, and change from DB baseline and OL baseline values, respectively of each vital sign parameters, weight, and BMI listed below:

- Systolic blood pressure (SBP) in supine and standing positions
- Diastolic blood pressure (DBP) in supine and standing positions
- pulse rate in supine and standing positions
- Orthostatic change in SBP
- Orthostatic change in DBP
- Orthostatic change in pulse rate
- Respiratory rate
- Temperature
- Body weight and BMI,

Percent change from DB baseline and OL baseline values in weight and BMI will be summarized in a similar way.

The number and percentage of subjects with Markedly Abnormal Vital Signs (MAVS), defined in [Table 9.1](#), will be presented by analysis group at DB baseline and OL baseline, post-OL baseline visits, endpoint, and any open-label treatment period (treatment-emergent, the worst case).

A listing of subject data for those who satisfy MAVS during the open-label treatment period will be presented.

Table 9.1: – Criteria for Markedly Abnormal Vital Signs and Weight

Parameter (unit)	Markedly Low	Markedly High
SBP (supine, standing) (mmHg)	<90	≥180
	Value ≤ 90 and ≥ 20 decrease from baseline	Value ≥ 180 and ≥ 20 increase from baseline
DBP (supine, standing) (mmHg)	<50	≥105
	Value ≤ 50 and ≥ 15 decrease from baseline	Value ≥ 105 and ≥ 15 increase from baseline
Pulse rate (supine, standing) (bpm)	<50	≥120
	Value ≤ 50 and ≥ 15 decrease from baseline	≥120 and increased >15 from baseline
Weight (kg)	≥ 7% decrease from baseline	≥ 7% increase from baseline
Temperature (°C)	N/A	Value ≥ 38.3°C and ≥0.8°C

		increase from baseline
Orthostatic Criteria		
SBP orthostatic criteria (mmHg)	≥ 20 mmHg reduction from supine to standing position	N/A
DBP orthostatic criteria (mmHg)	≥ 10 mmHg reduction from supine to standing position	N/A
Orthostatic tachycardia (bpm)	N/A	≥ 20 bpm increase from supine to standing position in pulse rate.

BMI measurements will be used to classify a subject’s weight status as underweight, normal, overweight or obese using [Table 9.2](#) and as underweight/normal, overweight, obesity class I, obesity class II, and obesity class III using [Table 9.3](#).

Shifts from OL baseline and shifts from DB baseline to endpoint for weight status categories ([Tables 9.3](#)) will be summarized by analysis group to show the number and percentage of subjects that fall into each category.

In addition, the number and percentage of subjects with 3%, 5%, 7%, and 10% reduction in body weight will be presented by visit and analysis group.

Table 9.2: – BMI Weight Status Category 1

BMI (kg/m ²)	Weight Status
< 18.5	Underweight
18.5 ≤ BMI < 25.0	Normal
25.0 ≤ BMI < 30	Overweight
≥ 30.0	Obese

Table 9.3: – BMI Weight Status Category 2

BMI (kg/m ²)	Weight Status
BMI < 25	Underweight/ Normal
25 ≤ BMI < 30	Overweight
30 ≤ BMI < 35	Obesity Class I
35 ≤ BMI < 40	Obesity Class II
40 ≤ BMI	Obesity Class III

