4.3. Risk-Benefit Assessment

Overall, in previous clinical studies dasotraline was generally safe and well tolerated. The pharmacokinetic (PK) and safety profiles observed in adults from completed clinical studies support evaluation of dose levels of 4 - 8 mg/day in adults with BED.

Most adverse events in completed clinical studies were mild to moderate in intensity, and included headache, dizziness, insomnia, tachycardia, and nausea. Dose dependent increases in the incidence of insomnia and weight loss were observed, consistent with DNRI pharmacology. A total of 13 serious adverse events (SAEs) have been reported in 9 subjects receiving dasotraline. Across the 8 completed clinical studies evaluating dasotraline, the rate of discontinuations as a result of treatment-emergent adverse events (TEAEs) was low. The highest rate of discontinuations due to TEAEs was in the SEP360-201 adult ADHD study (11.2% and 29.7% of subjects treated with dasotraline 4 and 8 mg/day, respectively), primarily due to insomnia. In general, the side-effect profile of dasotraline, based on available data, appears comparable with other medications used in the treatment of ADHD and suggests it may be well tolerated in patients with BED. A flexible dose design to reach the 8 mg dose will be implemented in this study to facilitate management of safety and tolerability issues.

The results from the human abuse liability study indicate dasotraline has minimal abuse potential and is unlikely to be recreationally abused. All doses of dasotraline (8, 16, 36 mg) demonstrated significantly lower drug liking scores than methylphenidate (40, 80 mg) and were no greater than placebo. The most frequently reported abuse potential adverse events were insomnia and dizziness in subjects with major depressive disorder (MDD) and insomnia and suicidal ideation in adults with ADHD. The current study will be conducted in accordance with relevant regulatory guidance and law with regards to handling, distribution, storage, dispensation, accountability, and destruction of study drug. In addition a comprehensive Abuse Potential Monitoring Plan (APMP) for dasotraline designed to detect potential abuse of the compound and to more closely monitor adverse events (AEs) consistent with the pharmacology of the compound will be implemented for this study (Section 24, Appendix V).

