6.1.4. Endpoint

6.1.4.1. Endpoint

Endpoint (ie, Week 52 Endpoint) is defined as the last post-OL Baseline assessment during the open-label treatment period.

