6.1.12. Subgroup Analysis

For a limited number of descriptive analyses, data will be presented for analysis group by subgroup below as needed:

- Age group at OL Baseline (years): “< 40 years”, “≥ 40 years”
- Gender: Male, Female
- Race: White, Non-white
- BMI at OL Baseline: Non-obese (ie, Normal & Overweight), Obese class I/II, Obese class III

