7.1.1. Demographic and Baseline Characteristics

Demographic and baseline characteristics will be summarized by analysis group and analysis subgroup based on the safety population.

Baseline descriptive statistics (N, mean, SD, median, and range) of demographic characteristics will be provided by analysis group and analysis subgroup for age at study entry (in years), body weight, height, body mass index (BMI, calculated as weight (kg)/ [height (m) ²]), and waist circumference.

The number and percentage of subjects in each of the following categories (and sub-categories) at baseline will also be summarized by analysis group:

- Age group: <40, ≥40 years old;
- Gender: Male, Female;
- Race: white, black or African American, Asian, American Indian or Alaska Native, Native Hawaiian or other Pacific Islander, Other;
- Ethnicity: Hispanic or Latino, Not Hispanic or Latino;
- Baseline BMI category : Underweight/Normal (<25), Overweight (25 to <30), Obesity Class I (30 to <35), Obesity Class II (35 to <40), and Obesity Class III (≥ 40) kg/m²;

Baseline summary statistics (N, mean, SD, median, and range) of disease characteristics will be provided by analysis group

- DB Baseline and OL Baseline of BE-CGI-S score
- DB Baseline and OL Baseline of EDE-Q modified global score and subscale scores

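### SAP 7.4.5.1 defines an underweight BMI category that no named summary uses, so newly underweight subjects are not counted by analysis group in any specified table

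*SAP*

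**What the plan says.** SAP 7.4.5.1 sets out two BMI classifications. The first sorts a subject's "weight status as underweight, normal, overweight or obese using" Table 9.2, titled "BMI Weight Status Category 1", where underweight is BMI below 18.5 and normal is 18.5 to below 25. The second uses Table 9.3, whose lowest row, "Underweight/ Normal", takes in everything below 25 and which then splits obesity into three classes.

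One categorical BMI output is named: "Shifts from OL baseline and shifts from DB baseline to endpoint for weight status categories", with a cross-reference to Table 9.3 only. SAP 6.1.4.1 says that Endpoint "is defined as the last post-OL Baseline assessment during the open-label treatment period". It is therefore the last value, not the lowest.

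Other places where BMI or weight is categorised:
- SAP 7.1.1, baseline categories: "Underweight/Normal (<25), Overweight (25 to <30"), followed by the three obesity classes.
- SAP 6.1.12, subgroups at OL baseline: "Non-obese (ie, Normal & Overweight), Obese class I/II, Obese class III".
- SAP Table 9.1: a weight change of 7% or more in either direction, with no BMI criterion.
- SAP 7.4.5.1: numbers with 3%, 5%, 7% and 10% weight reduction by visit, whatever the BMI.
- SAP 7.4.5.2, withdrawal period: descriptive statistics only.

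**The concern.** The plan defines a category for low BMI and then reports it nowhere by name. In the one BMI shift table, a subject can pass from normal to underweight without leaving the first row. A subject who goes from overweight to underweight is tabulated with those who go from overweight to normal, so a possible harm is pooled with a possible benefit. Because the shift stops at Endpoint, a fall below 18.5 that later reverses would not appear there even if the categories were separated.

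Body weight and BMI are part of the primary objective (Protocol 5.1, SAP 2.1). Protocol 4.3 says of earlier studies: "Dose dependent increases in the incidence of insomnia and weight loss were observed, consistent with DNRI pharmacology". Treatment lasts 12 months in people with an eating disorder, and the entry criteria of this protocol (8.1 and 8.2) set no lower BMI limit. A reader of the study report would reasonably want to know how many subjects became underweight in each analysis group.

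**Working it through.** The plan states no figure to reproduce here. The check applies the SAP's own cut-offs to assumed BMI values.

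**Inputs.** The underweight limit is 18.5 (Table 9.2). The merged lowest row is below 25 (Table 9.3). The weight-loss flag is 7% or more (Table 9.1). Height is fixed at the core-study Screening value (SAP 6.1.13), so a percentage change in weight equals the same percentage change in BMI.

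**Step 1: the two classifications side by side (assumed BMI pairs).**

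| BMI change | Table 9.3 (used in the shift) | Table 9.2 (not used) |
|---|---|---|
| 22 to 18.0 | Underweight/Normal, no change | Normal to Underweight |
| 24.5 to 18.4 | Underweight/Normal, no change | Normal to Underweight |
| 26 to 18.4 | Overweight to Underweight/Normal | Overweight to Underweight |
| 26 to 24 | Overweight to Underweight/Normal | Overweight to Normal |

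The last two rows fall in the same Table 9.3 cell. Anyone starting between 18.5 and just under 25 can become underweight with no recorded shift.

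**Step 2: loss needed to reach 18.5.** Loss = 1 − 18.5/starting BMI.

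| Assumed starting BMI | Loss needed |
|---|---|
| 19 | 2.6% |
| 19.5 | 5.1% |
| 20 | 7.5% |
| 21 | 11.9% |
| 22 | 15.9% |
| 24 | 22.9% |
| 24.99 | 26.0% |

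**Step 3: can the percentage-loss outputs stand in?** The highest starting BMI from which a loss r reaches 18.5 is 18.5/(1 − r).
- r = 7%: 18.5/0.93 = 19.9.
- r = 10%: 18.5/0.90 = 20.6.

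This cuts both ways. Anyone at 19.9 or above at the reference baseline must lose at least 7% to fall below 18.5 and so will carry the Table 9.1 flag. A subject starting between 18.5 and about 19.9 can cross without it. Conversely, the flag does not identify underweight: a 7% loss from an assumed BMI of 38 gives 38 × 0.93 = 35.3, and that subject is counted with the lean ones.

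**Step 4: worst-case reporting elsewhere.** The SAP already presents shifts to the worst case for suicidal ideation score (7.4.7.1) and for the neurological examination (7.4.8.2). The worst-case list in 6.1.5 includes the Table 9.1 criteria but no BMI category.

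**The case against.** The strongest reply is that the SAP exposes low BMI in other ways.
- BMI is summarised by visit with its range, which SAP Section 7 defines as minimum and maximum. A value below 18.5 that enters a by-visit summary lowers the displayed minimum for that group, including mid-study.
- All subject data are listed (6.2.1).
- The 7% weight-loss flag is tabulated by visit, at Endpoint and as worst case over the open-label period, with a listing. By Step 3 it catches everyone starting at BMI 19.9 or above, even if the weight is regained.
- Weight-related adverse events are a category of special interest (7.4.2).
- SAP Section 7 says that categorical data get counts and percentages, and Protocol 15.3.3.3 says much the same by visit. Together with the Table 9.2 classification, this could be read as a by-visit frequency of underweight.

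This reply defeats a stronger reading. A reader might infer that subjects who become underweight would be invisible, or that the report would show zero of them whatever happened. The documents do not support either inference: the data appear in several places, and no planned row is labelled newly underweight, so nothing would report a zero. The count is simply not specified.

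The reply does not supply that count. A minimum is one value per group and visit, a listing gives no incidence, and the flag mixes lean with obese subjects. The general rule on categorical data names neither Table 9.2 nor a shift from baseline, and would not give the lowest on-treatment value. Section 7 does mention selecting the worst result for shift analyses, but the BMI sentence names Endpoint only.

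Two further points have weight. The cross-reference in the shift sentence uses a plural noun with a single table number, so a reference to Table 9.2 may have been dropped by accident. The detailed obesity classes also suggest that few lean subjects were expected, which would make merging a sparse row understandable. Neither changes what the text now specifies.

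**Conclusion.** The point holds in this form: Table 9.2 is defined but no named summary uses it. The only BMI-category shift merges underweight with normal and runs to the last value, so newly underweight subjects are not counted by analysis group in any specified table. This is more than missing detail, because the stated rule puts a fall to underweight and a fall to normal weight in one cell for a measure named in the primary objective.

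The planned summaries of change and percent change in weight and BMI are complete and are not in question. The gap concerns the low tail only.

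The size cannot be computed. The documents give neither the BMI entry limits of the core studies nor a baseline BMI distribution, and every starting BMI above is an assumption. Under those assumptions the loss needed runs from 2.6% at BMI 19 to 26.0% at just under 25. The number affected may well be small. A small number is a reason to state it explicitly, since a few cases are easily lost in minima and listings. The change is worth making before database lock.

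**What to change.** In SAP 7.4.5.1:
1. Cite Table 9.2 alongside Table 9.3 in the shift summary, or split the first row of Table 9.3 into below 18.5 and 18.5 to below 25.
2. Present shifts from DB baseline and from OL baseline both to Endpoint and to the lowest BMI in the open-label treatment period, including unscheduled visits.
3. Add the number and percentage newly below 18.5 by analysis group, where newly means 18.5 or above at the baseline in question.

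The cost is one extra table, possibly with sparse cells. BMI is already derived at each visit (SAP 6.1.13), so no new data are needed.
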